3.2 Exclusion Criteria

- 1. Prior therapy:
 - a)
 - b) Prior therapy with a VEGF(R) inhibitor alone or in combination with immune checkpoint inhibitor(s).
 - c) Prior therapy with an anti-CTLA-4 antibody
- 2. Participants with active, known, or suspected autoimmune disease. Participants with type I diabetes mellitus, residual hypothyroidism due to autoimmune thyroiditis only requiring hormone replacement, skin disorders (such as vitiligo, psoriasis, or alopecia) not requiring systemic treatment are permitted to enroll.
- 3. Participants with a condition requiring systemic treatment with either corticosteroids (> 10 mg daily prednisone or equivalent) or other immunosuppressive medications within 14 days of study drug administration. Inhaled or topical steroids are permitted in the absence of active autoimmune disease.
- 4. History of allergy or hypersensitivity to any monoclonal antibody
- 5. Previous or concurrent malignancy within 3 years of study entry, with the following exceptions:
 - a) adequately treated basal or squamous cell skin cancer, superficial bladder cancer, prostate intraepithelial neoplasm, carcinoma in-situ of the cervix, or other noninvasive or indolent malignancy; OR
 - b) other solid tumors treated curatively in which the expected rate of recurrence within 5 years is < 5%.

CONFIDENTIAL - Cabozantinib + Nivolimab + Ipililumab Protocol Required Elements

- 6. Impaired cardiovascular function or clinically significant cardiovascular diseases, including any of the following:
 - History of acute coronary syndromes (including myocardial infarction, unstable angina, coronary artery bypass grafting, coronary angioplasty, or stenting) <6 months prior to screening,
 - Symptomatic congestive heart failure (i.e. Grade 2 or higher), history or current evidence of clinically significant cardiac arrhythmia and/or conduction abnormality <6 months prior to screening. Exceptions include asymptomatic/well-controlled atrial fibrillation/flutter or paroxysmal supraventricular tachycardia;
 - Uncontrolled hypertension defined as persistent elevation of systolic blood pressure ≥ 140 mmHg or diastolic blood pressure ≥ 90 mmHg, despite medical therapy
- 7. History of thromboembolic or cerebrovascular events ≤ 6 months prior to the first dose of study treatment. Examples include transient ischemic attacks, cerebrovascular accidents, hemodynamically significant (i.e., massive or sub-massive) deep vein thrombosis or pulmonary emboli.

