The below table provides treatment guidelines for hypertension deemed related to cabozantinib. Subjects with known hypertension should be optimally managed prior to entry into clinical trials with cabozantinib according to entry criteria of specific protocols. Blood pressure should be monitored in a constant position visit to visit, either sitting or supine in a relaxed setting. Decisions to reduce or interrupt the dose of study treatment must be based on BP readings taken by a medical professional and must be confirmed with a second measurement at least 5 minutes following the first measurement.

Cabozantinib should be discontinued in subjects with hypertensive emergency.

Management of Hypertension Associated with Cabozantinib

Event	Management	
Subjects NOT receiving optimized anti-hypertensive therapy		
> 140 mm Hg (systolic) ^a and < 160 mm Hg	Optimize antihypertensive medications by adding new or additional antihypertensive medications and/or increase dose of existing	
OR	medications.Reduce cabozantinib treatment by one dose level if optimal	
> 90 mm Hg (diastolic) and < 110 mm Hg	antihypertensive therapy (usually to include 3 agents) does not result in BP <140 mm Hg systolic or <90 mm Hg diastolic.	
	If subject is symptomatic interrupt cabozantinib treatment	
≥ 160 mm Hg (systolic)	Reduce cabozantinib by one dose level ^b or interrupt cabozantinib	
OR	treatment per Investigator discretion.Add new or additional anti-hypertensive medications and/or increase	
≥ 110 mm Hg (diastolic)	dose of existing medications and monitor subject closely for hypotension. If optimized antihypertensive therapy (usually to include 3 agents) does not result in BP < 140 mm Hg systolic or < 90 mm Hg	
	diastolic, cabozantinib treatment should be dose reduced further or interrupted.	
	Cabozantinib treatment should be dose interrupted if upper limits of systolic BP (≥ 160 mm Hg) are sustained and not adequately	
	manageable or if systolic BP is > 180 mm Hg or diastolic BP > 110 mm Hg, or if subject is symptomatic.	
	Re-start cabozantinib treatment at the most tolerable dose and	
	re-escalate only if BP falls to and is sustained at < 140 mm Hg systolic and < 90 mm Hg diastolic.	
Hypertensive emergency ^c	Discontinue cabozantinib treatment.	

^a Permitted dose levels are defined by individual protocols.

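### In the cabozantinib hypertension table both failure lines join the BP targets with *or*, so read literally a single raised value on optimized therapy does not count as failure

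*Combined protocol and SAP*

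**What the plan says.** All table lines below are from the protocol, Section 5.4.1.2.5 (Vascular Disorders), under Hypertension. The text introduces the table as treatment guidelines for hypertension judged related to cabozantinib.

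- **Row 1 entry:** systolic above 140 and below 160, *or* diastolic above 90 and below 110.
- **Row 1 actions:** add or increase antihypertensives. Then "Reduce cabozantinib treatment by one dose level if optimal" antihypertensive therapy (usually three agents) "does not result in BP <140 mm Hg systolic or <90 mm Hg diastolic". Separately, "If subject is symptomatic interrupt cabozantinib treatment".
- **Row 2 entry:** systolic 160 or more, *or* diastolic 110 or more.
- **Row 2 actions:** "Reduce cabozantinib by one dose level", or interrupt, on entry. If optimized therapy then misses the targets, stated with the same *or*, "cabozantinib treatment should be dose reduced further or interrupted".
- **Row 2 separate interruption line:** interrupt if systolic stays at 160 or more and cannot be managed adequately, or if systolic exceeds 180, diastolic exceeds 110, or the subject is symptomatic.
- **Row 2 re-escalation:** "re-escalate only if BP falls to and is sustained at < 140 mm Hg systolic and < 90 mm Hg diastolic".

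The dose steps in Section 5.4.1 are 40 mg daily, then 20 mg daily, then 20 mg every other day.

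**The concern.** A negated *or* is stricter than it looks. Saying that therapy did not bring systolic below 140 or diastolic below 90 means, taken literally, that it achieved neither. One value on target would then count as success, whatever the other value is.

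The two lines decide when cabozantinib is lowered for hypertension, which Section 5.4.1.2 lists among the most frequent adverse events with the drug. Isolated systolic or isolated diastolic elevation on treatment is the case in which the literal and the intended readings differ. At stake is whether two people applying the table to the same subject would take the same dose action.

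**Working it through.** The plan gives no figure to reproduce, and the check is one of logic. Let S and D be systolic and diastolic pressure on optimized therapy.

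**Step 1. The trigger under each wording.**

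- As written: NOT(S < 140 OR D < 90) = (S ≥ 140 AND D ≥ 90).
- With *and*: NOT(S < 140 AND D < 90) = (S ≥ 140 OR D ≥ 90).

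The two differ exactly when one value is on target and the other is not.

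**Step 2. Row 1, asymptomatic subject on the 40 mg starting dose.** The table shows the daily dose that the row's lines give.

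| BP on optimized therapy | As written | With *and* |
|---|---|---|
| 130/80 | 40 mg | 40 mg |
| 152/84 | 40 mg | 20 mg |
| 136/100 | 40 mg | 20 mg |
| 152/96 | 20 mg | 20 mg |

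No other row 1 line reduces the dose. The symptomatic line does not apply here. The gap is therefore systolic 140–159 with diastolic below 90, or diastolic 90–109 with systolic below 140.

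**Step 3. Row 2.** The reduction or interruption on entry does not depend on the failure line, so it stands under either wording. Take a subject who enters at 165/100 and is reduced from 40 to 20 mg daily:

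- BP falls to 150/94: the further step applies under both wordings.
- BP falls to 150/84: as written there is no further step. With *and*, the subject moves to 20 mg every other day or is interrupted.

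The separate interruption line narrows this gap. Consider whole-number pairs with systolic 100–220 and diastolic 60–130, asymptomatic, with exactly one value off target:

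- All such pairs: 81 × 30 + 41 × 40 = 2,430 + 1,640 = 4,070.
- Still caught by the interruption line, if every systolic of 160 or more is taken as sustained and unmanageable: 61 × 30 + 20 × 40 = 1,830 + 800 = 2,630.
- Not caught: 4,070 − 2,630 = 1,440. These are systolic 140–159 with diastolic below 90 (20 × 30 = 600) and diastolic 90–110 with systolic below 140 (21 × 40 = 840).

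These counts are grid cells that mark out the region. They are not expected patient frequencies.

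**Step 4. Size of a missed step.** In row 1 the ratio is 40/20 = 2. In row 2, 20 mg every other day averages 10 mg a day, so the ratio is 20/10 = 2. If the entry action in row 2 was an interruption, nothing more is lost until restart.

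**Step 5. Consistency within the table.** A subject at 152/84 is high enough to be in row 1 and too high to be re-escalated under row 2. Yet, on the literal wording, the same subject has not failed therapy. The entry and re-escalation lines agree with each other, and the failure lines are the exception.

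**The case against.** The strongest reply is that no careful clinician would read the lines this way. The *or* can be taken to echo the row entry, so that failure means the target for whichever value was raised was not met. The entry and re-escalation lines support that sense. This stands: the intended either-value meaning can be inferred, and the literal consequence is a risk of misreading, not a settled instruction.

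A reader might infer that subjects with one raised value have no safeguard, or that the protocol requires the higher dose to continue. The documents do not support either:

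- Row 1 still tells the investigator to intensify antihypertensives for a single raised value.
- Section 5.4.1 calls for reduction or interruption when toxicity is unacceptable, and lets the investigator act below the tabulated thresholds.
- The general dose-modification table in Section 5.4.1 directs reduction or interruption, at the investigator's discretion, for Grade 2 events that are intolerable and not adequately managed. For Grade 3 events it directs interruption unless a dose reduction and optimal care manage the event easily.
- Section 5.4.1.2 directs discontinuation for hypertension that stays uncontrolled on the best medical management.

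These are backstops and do not correct the two lines. The general table defers to Section 5.4.1.2 for specific conditions. The discretionary text sets no BP trigger. The discontinuation text does not define uncontrolled for subjects on treatment. The only definition is exclusion 6 in Section 3.2: "Uncontrolled hypertension defined as persistent elevation of systolic blood pressure ≥ 140 mmHg or diastolic blood pressure ≥ 90 mmHg, despite medical therapy". It is an either-value rule, but it governs entry only. If it were borrowed, a persistent 152/84 on optimal management could call for stopping the drug, while the table had not called for the milder one-level reduction.

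**Conclusion.** The point holds as a low-severity wording defect in a safety dose guideline. Both failure lines, read literally, require both values to be off target, and this is inconsistent with the table's own entry and re-escalation lines.

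On that reading, the row 1 reduction is missed for asymptomatic subjects on optimized therapy with exactly one value off target. In row 2 only the further step is at risk, and it is fully lost only in the two ranges in Step 3. That row 2 limit assumes that systolic pressures of 160 or more are sustained and unmanageable, so that the separate interruption line applies.

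Two stronger conclusions should not be drawn. A reader might infer that a row 2 subject escapes dose action altogether, but the entry action is unconditional. A reader might also infer that some number of subjects will receive twice the intended dose. The documents give no rate for these BP states, investigators may reduce at their discretion, and many would read the line as intended. The factor of 2 describes one missed step on the literal reading and nothing more. Alpha, power and sample size are unaffected.

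**What to change.** At the next amendment, replace *or* with *and* in both failure lines, so that the condition becomes: does not result in BP < 140 mm Hg systolic and < 90 mm Hg diastolic. Either value off target then triggers the step, which matches the re-escalation line.

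The cost is one word in each of two table cells. No assessments are added, because the Section 4.2 schedule already takes blood pressure at each visit.

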5.4.1.2.6 Stomatitis and Mucositis

Preventive measures may include a comprehensive oral examination to identify and treat any potential risk for complications before study treatment is initiated. Appropriate correction of local factors should be instituted as indicated, such as modification of ill-fitting dentures and appropriate care of gingivitis. During treatment with cabozantinib, good oral hygiene and standard local treatments such as non-traumatic and non-irritating cleansing, and oral rinses (e.g., with a weak solution of salt and baking soda) should be maintained. Lips should be kept moisturized with lip balm. The use of lipstick, lip-gloss, and Vaseline should be avoided.

b Hypertensive emergency is defined as uncontrolled elevated BP with clinical evidence of progressive or impending endorgan damage (e.g., myocardial infarction/ischemia, intracranial haemorrhage, cerebral ischemia, pulmonary edema, encephalopathy, kidney damage).

Local treatment should be instituted at the earliest onset of symptoms. Obtain bacterial/viral culture if oral infection is suspected and treat infection as clinically indicated.

5.4.1.2.7 Skin and Subcutaneous Tissue Disorders

Wound healing and surgery: Cabozantinib has the potential to cause wound healing complications and wound dehiscence which may even occur long after a wound has been considered healed. Therefore, surgical and traumatic wounds must not only be completely healed prior to starting cabozantinib treatment but must also be monitored for wound dehiscence, wound infection and other signs of impaired wound healing while the subject is being treated with cabozantinib. If dehiscence occurs, cabozantinib treatment should not be restarted until complete healing has taken place.

Treatment with cabozantinib should be stopped at least 3 weeks prior to elective surgery. Do not administer cabozantinib for at least 2 weeks after major surgery and until complete wound healing.

Palmar-plantar erythrodysesthesia syndrome (PPES; also known as hand-foot syndrome), skin rash (including blister, erythematous rash, macular rash, skin exfoliation, dermatitis acneiform, and papular rash), pruritus, dry skin, erythema, pigmentary changes, and alopecia have been reported with cabozantinib. All subjects on study should be advised on prophylactic measures including the use of emollients, removal of calluses, avoidance of exposure of hands and feet to hot water leading to vasodilatation, protection of pressure-sensitive areas of hands and feet, and use of cotton gloves and socks to prevent injury and keep the palms and soles dry.

Early manifestations include tingling, numbness, mild hyperkeratosis, and symmetrical red and swollen areas on the palms and soles. The lateral sides of the fingers or periungual zones may also be affected. Adequate interventions are required to prevent worsening of skin symptoms such as blisters, desquamations, ulcerations, or necrosis of affected areas. Analgesics may be required for pain control.

Aggressive management of symptoms is recommended, including early dermatology referral.

Management of Hand-Foot Syndrome (PPES) Associated with Cabozantinib

Event	Management
Grade 1	Cabozantinib treatment may be continued at the current dose if PPES is clinically insignificant and tolerable. Otherwise, cabozantinib should be reduced to the next lower dose level. Start urea 20% cream twice daily AND clobetasol 0.05% cream once daily. Reassess at least weekly; if PPES worsens at any time or does not improve after 2 weeks, proceed to the intervention guidelines for Grade 2.
Grade 2	Cabozantinib treatment may be continued if PPES is tolerated. Cabozantinib should be dose reduced or interrupted if PPES is intolerable. Continue urea 20% cream twice daily AND high potency steroid cream (e.g., clobetasol 0.05%) once daily and add analgesics (e.g., NSAIDs/gamma-aminobutyric acid agonists) for pain control if needed. Reassess at least weekly; if PPES worsens or affects self-care, proceed to the intervention guidelines for Grade 3.
Grade 3	Interrupt cabozantinib treatment until severity decreases to Grade 1 or 0. Continue treatment of skin reaction with high potency steroid cream (e.g., clobetasol 0.05%) twice daily AND analgesics. Resume cabozantinib at a reduced dose if PPES recovers to Grade ≤ 1. Discontinue subject from cabozantinib if PPES does not improve within 6 weeks.
^a Permitted dose	levels are defined by individual protocols.

5.4.1.2.8 Angioedema

Angioedema should be managed according to standard practice. The subject should be observed until symptoms resolve, with particular attention to maintaining an open airway.

5.4.1.2.9 Osteonecrosis

Osteonecrosis has been reported in subjects treated with cabozantinib. Additional risk factors include use of bisphosphonates and denosumab, chemotherapy and anti-angiogenic drugs, use of corticosteroids, local radiotherapy, and dental or orofacial surgery procedures.

Osteonecrosis of the jaw (ONJ) can manifest as jaw pain, osteomyelitis, osteitis, bone erosion, tooth or periodontal infection, toothache, gingival ulceration, or gingival erosion. Persistent pain or slow healing of the mouth or jaw after dental surgery may also be manifestations of osteonecrosis.

Perform an oral examination prior to initiation of cabozantinib and periodically during cabozantinib treatment. Advise subjects regarding oral hygiene practice and to quickly report symptoms to Investigator. Caution should be used in subjects receiving bisphosphonates.

Invasive dental procedures should be avoided. In cases where dental procedures are unavoidable, treatment with cabozantinib should be interrupted for at least 3 weeks prior to the procedure and resumed after complete wound healing has occurred. Bone healing may often require a protracted time.

Withhold cabozantinib for development of ONJ until complete resolution.

5.4.1.2.10 Proteinuria

Proteinuria has been reported with cabozantinib. Proteinuria should be monitored by measuring UPCR. The below table provides treatment guidelines for proteinuria deemed related to cabozantinib.

Cabozantinib should be discontinued in subjects who develop nephrotic syndrome (proteinuria > 3.5 grams per day in combination with low blood protein levels, high cholesterol levels, high triglyceride levels, and edema).

Management of Proteinuria Associated with Cabozantinib

Event	Management
UPCR ≤ 1 mg/mg (≤ 113.1 mg/mmol)	No change in cabozantinib treatment or monitoring.
UPCR > 1 and < 3.5 mg/mg (> 113.1 and < 395.9 mg/mmol)	 Consider confirming with a 24-h protein assessment within 7 days. No change in cabozantinib treatment required if UPCR ≤ 2 mg/mg or urine protein ≤ 2 g/24 h on 24-h urine collection. Dose reduce or interrupt cabozantinib treatment if UPCR > 2 mg/mg on repeat UPCR testing or urine protein > 2 g/24 h on 24-h urine collection. Continue cabozantinib on a reduced dose if UPCR decreases to < 2 mg/mg. Consider interrupting cabozantinib treatment if UPCR remains > 2 mg/mg despite a dose reduction until UPCR decreases to < 2 mg/mg. Restart cabozantinib treatment at a reduced dose after a dose interruption. Repeat UPCR within 7 days and once per week. If UPCR < 1 mg/mg on 2 consecutive readings, UPCR monitoring can revert to protocol-specific times. (Second reading is confirmatory and can be done within 1 week of first reading.) If UPCR remains > 1 mg/mg and < 2 mg/mg for 1 month or is determined to be stable (< 20% change) for 1 month, check urine protein/creatinine per protocol or as clinically indicated.
UPCR ≥ 3.5 mg/mg (≥ 395.9 mg/mmol)	 Interrupt cabozantinib treatment pending repeat UPCR within 7 days and/or 24-h urine protein. If ≥ 3.5 mg/mg on repeat UPCR, continue to hold cabozantinib treatment and check UPCR every 7 days. If UPCR decreases to < 2 mg/mg, restart cabozantinib treatment at a reduced dose and monitoring of urine protein/creatinine should continue weekly until the UPCR decreases to < 1 mg/mg. If UPCR remains > 1 mg/mg and < 2 mg/mg for 1 month or is determined to be stable (< 20% change) for 1 month, check urine protein/creatinine per protocol or as clinically indicated.
Nephrotic syndrome	Discontinue cabozantinib treatment.

5.4.1.2.11 Nervous System Disorders

Cabozantinib appears to represent minimal risk of adverse neurological effects based on nonclinical Good Laboratory Practice (GLP)-compliant toxicology studies. Dysphonia, dysgeusia, headache, dizziness, confusional state, convulsion, depression, memory impairment, hypoesthesia, peripheral neuropathy, insomnia, ataxia, and encephalopathy have been observed in clinical studies with cabozantinib. The development of any new or progressive, unexplained neurological symptoms should be assessed for underlying causes. RPLS has been reported.

RPLS should be considered in any subject presenting with seizures, headache, visual disturbances, confusion or altered mental function. Cabozantinib treatment should be discontinued in subjects with RPLS.

5.4.1.2.12 Infections and Infestations

Infections are commonly observed in cancer subjects. Predisposing risk factors include a decreased immune status (e.g., after myelosuppressive anticancer therapies, splenectomy), destructive growth of the underlying malignancy including bone marrow infiltration with suppression of normal hematopoiesis, as well as the presence of IV devices.

Infections and abscesses should be treated with appropriate local care and systemic therapy. Cabozantinib should be interrupted until complete healing has taken place.

5.4.1.2.13 Blood and Lymphatic System Disorders

Hematological toxicities (i.e., neutropenia, thrombocytopenia, and anemia) and associated complications have been observed after administration of cabozantinib and may be managed with dose interruptions and/or dose reductions. Subjects with hematologic toxicities may require additional or more frequent laboratory tests according to institutional guidelines.

Dose reductions or dose interruptions for hematological toxicities are not mandated but can be applied as clinically indicated. Supportive care for thrombocytopenia or anemia, such as transfusions, may be managed according to institutional guidelines. The use of colony-stimulating growth factors should be considered. Febrile neutropenia or evidence of infection associated with neutropenia must be assessed immediately and treated appropriately and in a timely manner according to institutional guidelines.

5.4.1.2.14 Fatigue

Common causes of fatigue, such as anemia, deconditioning, emotional distress (depression and/or anxiety), poor nutrition, dehydration, sleep disturbance, and hypothyroidism should be ruled out and treated according to standard of care. Pharmacological management should be considered after disease specific morbidities have been excluded when not prohibited.

